6.5. Baseline and Other Summaries and Analyses

6.5.1. Baseline Summaries

The demographic characteristics will be summarized by treatment group within the FAS. This will include age, gender, race, ethnicity baseline height, and baseline weight. All baseline disease characteristics will be summarized by treatment group within the FAS.

6.5.2. Study Conduct and Participant Disposition

Participant evaluation groups will be presented for all screened participants, and participant disposition will be summarized within the FAS population. The number of participants screened and randomized will be presented. The number of participants treated, completing and discontinuing by study phase, as well as the number of participants in each analysis set will be summarized by treatment group. For participants who did not complete the study, the reasons for withdrawal from the study will be presented.

In addition, the number of participants who were excluded from the PP analysis set will be summarized by reasons for the exclusion.

6.5.3. Study Treatment Exposure

Duration of treatment will be summarized within SAS population.

The duration of treatment will be calculated as follows: Duration of treatment = Date of last dose of study drug - date of first dose of study drug +1.

6.5.4. Prior and Concomitant Medications

The frequency of prior and concomitant medications will be summarized by treatment based on the WHO-drug coding dictionary within SAS population in accordance with Clinical Data Interchange Standards Consortium (CDISC) and Pfizer Standards (CaPS).

6.6. Safety Summaries and Analyses

Standard summary tables and listings will be generated in accordance with Clinical Data Interchange Standards Consortium (CDISC) and Pfizer Standards (CaPS) for safety reporting for the following parameters: adverse events, lab parameters, vital signs, discontinuations from study, discontinuations from treatment, and treatment duration.

6.6.1. Adverse Events

All adverse events will be coded according to the Medical Dictionary for Regulatory Activities (MedDRA) and will be summarized by treatment group within SAS population. Only TEAE summaries to AEs that started on or prior to Day 34 will be summarized. A list of pre-specified AESIs is provided in [Appendix 5](#).

6.6.2. Subgroup Analysis of Adverse Events and Serious Adverse Events

A subgroup analysis of treatment emergent AEs and SAEs will be provided by vaccination status.

6.6.3. Laboratory Data

Descriptive statistics will be summarized by treatment group as well as mean change from baseline for laboratory parameters within SAS population.

Laboratory shift tables from baseline will be presented for the following laboratory abnormalities at baseline: D-dimer levels, Liver function tests (ALT/AST), Creatinine Clearance (derived using Cockcroft-Gault Equation), TSH, T4 (free), fibrinogen, platelets, PT, aPTT, albumin, and total proteins.

All laboratory data will be reported in accordance with Clinical Data Interchange Standards Consortium (CDISC) and Pfizer Standards (CaPS) for safety reporting.

6.6.4. Vital Signs

The measurement taken immediately prior to start of study drug will be used as the baseline for calculating change from baseline.

All vital signs data will be descriptively summarized by treatment group within SAS population and reported in accordance with Pfizer data standard for safety reporting.

7. INTERIM ANALYSES

7.1. Interim Analyses and Summaries

There were 3 interim analyses as follows:

First interim analysis (45% planned enrollment through Protocol Amendment 4): An interim analysis was conducted for efficacy, futility and sample size re-estimation, and reviewed by an independent E-DMC after a prespecified accrual of participants (ie, approximately 45% overall participants have completed Day 28 efficacy assessment in the mITT population), according to the SAP and E-DMC charter. The sample size could be increased one time and the increase is limited to 30 to 35%. A well-established method described by Cui, Hung, and Wang (1999)² (implemented in EAST 6.5) would be used to control the Type I error probability.³

The nominal significance level for the interim and final time to sustained alleviation of all targeted COVID-19 signs/symptoms analyses was determined by means of the Lan-DeMets procedure with an O'Brien-Fleming stopping boundary, with an overall 2-sided type I error rate of 5%.

O'Brien-Fleming approach was used for decision making, ie, reject H_0 with 2-sided p-value ≤ 0.002 , or reject H_1 with 2-sided p-value > 0.924 at the formal interim analysis. At the final analysis, the p-value for rejecting H_0 will be ≤ 0.049 (2-sided) or reject H_1 with 2-sided p-value > 0.049 will be considered.

Before any interim analysis was performed, the details of the objectives, decision criteria, dissemination plan, and method of maintaining the study blind as per Pfizer's SOPs was documented and approved in an E-DMC charter.

The first interim analysis (45% planned enrollment through Protocol Amendment 4) summarized above was performed as described.

Second interim analysis (80% planned enrollment through Protocol Amendment 4): Upon review of the 45% analysis, the E-DMC requested the Sponsor to consider appropriate course of action for the ongoing trial to assess the clinical benefit. In order to respond properly to fulfill the E-DMC recommendation, the RRP decided that a second interim analysis should be conducted to address the E-DMC's request. This resulted in the analysis of 80% of enrolled participants through Protocol Amendment 4, without any adjustment to the alpha.

Third interim analysis (100% planned enrollment through Protocol Amendment 4): A third interim analysis was completed on enrolled participants who had risk factors for severe COVID-19 illness (ie, vaccinated against the SARS-CoV-2 virus) as well as participants who did not have risk factors for severe COVID-19 illness (ie, not vaccinated). Data from the study are required to support regulatory submissions thereby necessitating an interim analysis utilizing the 19 December 2021 dataset. This dataset had not been analyzed previously because the protocol was amended to increase the sample size and extend enrollment to assess the potential benefit of participants at low risk of progression to severe

COVID-19 in the clinically relevant endpoint of hospitalization or death (Protocol Amendment 5, 21 January 2022). The participants who were vaccinated are considered the high risk population and the unvaccinated participants are considered standard risk in the statistical analysis.

7.2. Data Monitoring Committee

This study will use an E-DMC. The E-DMC is independent of the study team and includes only external members. The E-DMC charter describes the role of the DMC in more detail.

The E-DMC will be responsible for ongoing monitoring of the efficacy and safety of participants in the study according to the charter. The recommendations made by the E-DMC will be forwarded to the appropriate authorized Pfizer personnel for review and final decision. Pfizer will communicate such decisions, which may include summaries of aggregate analyses of safety data to regulatory authorities, investigators, as appropriate.

7.3. Blinding of the Sponsor

The majority of sponsor staff will be blinded to study intervention allocation. There will be an unblinded team supporting the interactions with, and the analyses for, the E-DMC while the study is ongoing. The team will consist of medical monitor/clinicians, reporting statistician and reporting programmer(s) and will be separate from the direct members of the study team. The reporting team may include designated ad hoc member(s).

After all participants complete the Day 34 visit (or Early Termination (ET) prior to Day 34 visit), the study will be unblinded and analyses through Day 34, including the primary efficacy endpoint analyses, will be conducted. A blinded team will remain in place to monitor and manage the study until primary completion date is attained (all participants have reached Day 34 visit or discontinued prior to Day 34 visit).

Details of the unblinded sponsor staff supporting the E-DMC and the timing of unblinding will be outlined in the Unblinding Plan.

9. APPENDICES

Appendix 1. Summary of Efficacy Analyses

Endpoint	Analysis Type	Population	Data Inclusion and Rules for Handling Intercurrent Events and Missing Data	Analysis Model
Time (days) to sustained alleviation of all targeted COVID-19 signs/symptoms through Day 28.	Primary efficacy Analysis	mITT1	All data collected will be included. Missing severity at baseline will be treated as mild. Other missing data will be estimated with KM (lifetest) procedure	Kaplan-Meier & Log rank test
Time (days) to sustained alleviation of all targeted COVID-19 signs/symptoms through Day 28.	Sensitivity analysis for primary endpoint	mITT1	All data collected will be included. Missing severity at baseline will be treated as mild.	Cox proportional hazard model
Time (days) to sustained alleviation of all targeted COVID-19 signs/symptoms through Day 28.	Sensitivity analysis for primary endpoint	mITT1 exclude site 1488	All data collected will be included. Missing severity at baseline will be treated as mild.	Cox proportional hazard model
Time (days) to sustained alleviation of all targeted COVID-19 signs/symptoms through Day 28.	Supplemental analysis for primary endpoint	PP	Participants who discontinued the study before Day 28 without event will be censored at Day 25.	Kaplan-Meier & Log rank test
Time (days) to sustained alleviation of all targeted COVID-19 signs/symptoms through Day 28.	Sensitivity analysis for Primary Efficacy analysis for multiple enrollers	mITT1 including only data with first randomization within the study	All data collected will be included regardless of intercurrent events. Kaplan-Meier method to take account of losses to follow-up.	Kaplan-Meier method
Time (days) to sustained alleviation of all targeted COVID-19 signs/symptoms through Day 28 by vaccination status	Subgroup analysis for primary endpoint	mITT1	Use baseline variables as described in Section 6.4.	Cox proportional hazard model
Proportion of participants with COVID-19 related hospitalization or death from any cause through Day 28	Key secondary analysis	mITT1	All data collected will be included regardless of intercurrent events. Kaplan-Meier method to take account of losses to follow-up.	Kaplan-Meier method
Proportion of participants with COVID-19 related hospitalization or death from any cause through Day 28	Sensitivity analysis for key secondary endpoint	mITT1	If the participant's last observed data is prior to Day 21, then impute as an event with event day as day of last observed data +1. If the participant's last observed data is on or after Day 21, do not impute an event and	Kaplan-Meier method

Endpoint	Analysis Type	Population	Data Inclusion and Rules for Handling Intercurrent Events and Missing Data	Analysis Model
			participant remains censored at day of last observed data.	
Proportion of participants with COVID-19 related hospitalization or death from any cause through Day 28	Sensitivity analysis for key secondary efficacy analysis for multiple enrollers	mITT1 including only data with first randomization within the study	All data collected will be included regardless of intercurrent events. Kaplan-Meier method to take account of losses to follow-up.	Kaplan-Meier method
Proportion of participants with COVID-19 related hospitalization or death from any cause through Day 28 by vaccination status	Subgroup analysis for key secondary endpoint	mITT1	Subset analysis identified in Section 6.4.	Kaplan-Meier method
Proportion of participants with COVID-19 related hospitalization or death from any cause through Day 28	Supplemental analysis for key secondary efficacy endpoint	PP	Participants who discontinued the study before Day 28 without event will be censored at Day 25.	Kaplan-Meier & Log rank test
Proportion of participants with death (all cause) through Week 24.	Secondary analysis	mITT1	All data collected will be included regardless of intercurrent events exclude participants enrolled under PA6	Logistic Regression
Number of COVID-19 related medical visits through Day 28.	Secondary analysis	mITT1	All data collected will be included regardless of intercurrent events. Missing data will not be imputed.	Descriptive statistics (based on negative Binomial Model)
Number of days in hospital and ICU stay in participants with COVID-19 related hospitalization through Day 28.	Secondary analysis	mITT1	All data collected will be included regardless of intercurrent events. Missing data will not be imputed.	Descriptive statistics
Proportion of participants with severe signs/symptoms attributed to COVID-19 through Day 28.	Secondary Efficacy Analysis	mITT1	All data collected will be included regardless of intercurrent events, LOCF for missing data.	Logistic regression model
Proportion of participants with any severe targeted signs/symptoms attributed to COVID 19 at Day 1(baseline).	Supplemental analysis for secondary endpoint	mITT1	Any severe (ie, any targeted symptoms with severe baseline score) LOCF for missing data.	Logistic regression model
Proportion of participants with any severe targeted signs/symptoms	Supplemental analysis for secondary endpoint	mITT1	Any severe (ie, any targeted symptoms with severe baseline score) LOCF for missing data.	Logistic regression model

Endpoint	Analysis Type	Population	Data Inclusion and Rules for Handling Intercurrent Events and Missing Data	Analysis Model
attributed to COVID 19 from Day 2 to Day 6 (during treatment)				
Proportion of participants with any severe targeted signs/symptoms attributed to COVID 19 from Day 7 to Day 28 (post treatment)	Supplemental analysis for secondary endpoint	mITT1	Any severe (ie, any targeted symptoms with severe baseline score) LOCF for missing data.	Logistic regression model
Proportion of participants with severe signs/symptoms attributed to COVID 19 through Day 28.	Supplemental analysis for secondary endpoint	mITT1	Observed proportions for each targeted signs and symptom with severe category only will be plotted over time through Day 28. Additionally, observed proportion of participants reporting the presence of each targeted sign and symptom that is mild, moderate or severe categories will also be presented	Plot/Figure
Time (days) to sustained resolution of all targeted COVID-19 signs/symptom through Day 28.	Secondary analysis	mITT1	All data collected will be included. Missing severity at baseline will be treated as mild. Other missing data will be estimated with KM (lifetest) procedure	Kaplan-Meier & Log rank test
Duration of each targeted COVID-19 sign/symptom.	Secondary analysis	mITT1	All data collected will be included regardless of intercurrent events. Missing data will not be imputed.	Kaplan-Meier estimate, Descriptive statistics (median, quartiles)
Progression to a worsening status in 1 or more self-reported COVID19 associated symptoms through Day 28.	Secondary analysis	mITT1	All data collected will be included regardless of intercurrent events. Missing severity at baseline will be treated as mild.	Logistic regression model
Progression to a expanded worsening status in 1 or more self-reported COVID19 associated symptoms through Day 28.	Secondary analysis	mITT1	All data collected will be included regardless of intercurrent events. Missing severity at baseline will be treated as mild.	Logistic regression model
Proportion of participants with a resting peripheral oxygen saturation $\geq 95\%$ at Days 1 and 5.	Secondary analysis	mITT1	All data collected will be included regardless of intercurrent events. Missing data will not be imputed.	Breslow-Day test for Homogeneity of the Odds Ratios
Viral titers measured via RT-PCR in nasal swabs over time.	Secondary analysis	mITT1	All data collected will be included regardless of intercurrent events. If visit data in viral load is missing, the earliest measurement	MMRM analysis

Endpoint	Analysis Type	Population	Data Inclusion and Rules for Handling Intercurrent Events and Missing Data	Analysis Model
			closest to the visit will be used for the visit.	
Viral titers measured via RTPCR in nasopharyngeal samples at Day 1 and Day 5.	Sensitivity analysis (POC)	mITT1	All data collected will be included regardless of intercurrent events. Use baseline viral load (continuous).	ANCOVA analysis
CCI [REDACTED]	CCI [REDACTED]	CCI [REDACTED]	CCI [REDACTED]	CCI [REDACTED]

* All: Combining mITT1 population from before and after Protocol Amendment #6, dated 09 Jun 2022.

Pre-PA5: mITT1 population from before Protocol Amendment #5, dated 21 Jan 2022,

Post-PA5: mITT1 population from after Protocol Amendment #5, dated 21 Jan 2022

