4. ANALYSIS SETS (POPULATIONS FOR ANALYSIS)

Data for all participants will be assessed to determine if participants meet the criteria for inclusion in each analysis population prior to unblinding and releasing the database and classifications will be documented per standard operating procedures.

Population	Description
Full Analysis Set (FAS)	All participants randomly assigned to study intervention regardless of whether or not study intervention was administered.
Safety Analysis Set (SAS)	All participants who receive at least 1 dose of study intervention. Participants will be analyzed according to the intervention they actually received. A randomized but not treated participant will be excluded from the safety analyses.

Population	Description
Modified Intent -To Treat (mITT)	All participants randomly assigned to study intervention who take at least 1 dose of study intervention and with at least 1 postbaseline visit through Day 28 who were treated ≤ 3 days after COVID symptoms onset. Participants will be analyzed according to the study intervention to which they were randomized.
Modified Intent-To-Treat (mITT1)	All participants randomly assigned to study intervention, who take at least 1 dose of study intervention. Participants will be analyzed according to the study intervention they were randomized.
Per-Protocol (PP)	All participants in the mITT1 set without important protocol deviations considered to impact the interpretation of the primary efficacy endpoint. Protocol deviations will be reviewed to generate the list of participants with significant deviations to be excluded from the PP analysis set. The PP exclusion criteria will be finalized prior to breaking the blind.

Both the mITT1 and PP analysis sets will be used in the analyses of the primary efficacy endpoint, with the mITT1 being primary. For proportion of COVID-19 related hospitalization or death from any cause and all other efficacy endpoints, mITT1 will be used. The Safety Analysis Set will be used in the analyses of the safety data.

Multiple Enrollers:

If a participant enters/is randomized into Study C4671002 more than once or is enrolled in Study C4671002 and in 1 or 2 other Phase 2/3 nirmatrelvir/ritonavir studies:

- (1) The primary and key secondary efficacy analyses will be performed by considering all enrolled participants (subject IDs) as independent participants.

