6. ANALYSES AND SUMMARIES

6.1. Primary Endpoint

6.1.1. Primary Endpoint/Estimand Analysis

6.1.1.1. Main Analysis

The primary endpoint is time (days) to sustained alleviation of all targeted COVID-19 signs/symptoms through Day 28 in the mITT1 population.

Sustained alleviation of all targeted COVID-19 signs/symptoms is defined as the event occurring on the first of 4 consecutive days when all symptoms scored as moderate or severe at study entry are scored as mild or absent AND all symptoms scored mild or absent at study entry are scored as absent. The first day of the 4 consecutive-day period will be considered the First Event Date.

For symptoms with no reported severity in baseline, the symptom will have to be absent in order to be counted as sustained alleviated/resolved (missing severity at baseline will be treated as mild).

Day 25 is the last possible day the symptom alleviation and resolution endpoints can be achieved (definition includes data from the subsequent three days) and Day 28 is the last day participants report their daily signs and symptoms.

The time to sustained symptom alleviation/resolution for the purpose of this study is defined as:

- For a participant with sustained symptom alleviation/resolution (event), time to event will be calculated as (First Event Date) – (First Dose Date) +1.

- For a participant that either completes Day 28 of the study or discontinues from the study before Day 28 without sustained symptom alleviation/resolution (censored), censoring date will be at the last date on which symptom alleviation/resolution is assessed, and time will be calculated as (Censoring Date) – (First Dose Date) +1 or Day 25 whichever occurs first.

The decision to require 4 consecutive days of all targeted symptoms alleviation/resolution was based on exploratory analyses of data from the ACTIV-2/A5401 study, which suggested that this choice (rather than requiring fewer consecutive days) better captured sustained symptom resolution with low probability of subsequent relapse.

Participants who are hospitalized for the treatment of COVID-19 or death from any cause during the 28-day period will be classified as not achieving sustained symptom alleviation and will be censored at Day 25.

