6.1.1.2. Sensitivity and Supplemental Analyses

Sensitivity analyses will be performed to the primary efficacy endpoint:

The primary efficacy analyses will also be conducted using the PP population as supplemental analyses.

The primary endpoint will also be analyzed in which participants who discontinued the study before Day 28 without event will be censored at Day 25.

For sensitivity analysis of primary endpoint, Cox proportion hazard models with terms including treatment and treatment strata (ie, region, vaccination, baseline serology, baseline viral load $<10^4$ copies/mL vs $\geq 10^4$ copies/mL). These factors will be used to estimate the hazard ratio (the ratio of alleviation of all targeted signs and symptoms) and its 95% CI. Additional analyses may be performed adjusting for baseline covariates (such as age, gender, etc) as additive terms to the primary model, if necessary.

Based on FDA request, a sensitivity analysis excluding participants only from Site 1488 will be conducted as well.

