6.2.2. Incidence of SAEs and AEs Leading to Discontinuations

The incidence of SAEs and AEs leading to discontinuation will be summarized by treatment group using the SAS population.

6.2.3. Proportion of Participants with COVID-19 Related Hospitalization or Death From Any Cause Through Day 28

The estimand for proportion of participants experiencing COVID-19 related hospitalization or death from any cause through Day 28 is the difference in proportions of participants experiencing COVID-19 related hospitalization or death from any cause through Day 28 in nonhospitalized adult patients with COVID-19 who are at low risk of progression to severe disease and were treated ≤ 5 days after COVID-19 symptom onset. This will be estimated irrespective of adherence to randomized treatment.

The statistical methodology for proportion of participants with COVID-19 related hospitalization or death from any cause through Day 28 will be as follows:

The cumulative proportion of participants hospitalized for the treatment of COVID-19 or death during the first 28 days of the study will be estimated for each treatment group using the Kaplan-Meier method to take account of lost to follow-up and summarized graphically for each treatment group. The estimand is the difference of the proportions in the 2 groups and its 95% CI will be presented, as well as, the associated two sample proportion test (Wald test results). For the 95% CI, the corresponding estimate of the standard error is computed using Greenwood's formula⁴. The Greenwood's formula to estimate the variance of the difference of proportions at Day 28 is $[\text{Var}(S_{PF}(28)) + \text{Var}(S_{\text{Placebo}}(28))]$. Instead of dealing with $S(t_i)$ the log-log approach to CI will be used. The 95% CI will be computed for the estimate of $L(t) = \log(-\log(S(t)))$, the log hazard function.

The CI will be in the right range when transformed back to $S(t) = \exp(-\exp(L(t)))$. Antilogging this CI will give a 95% confidence interval for the difference itself.

A sensitivity analysis for proportion of participants with COVID-19 related hospitalization or death from any cause through Day 28 will be provided using mITT1 as follows:

For participants with missing data due to lost to follow up for COVID-19 related hospitalization or death from any cause, the sensitivity analysis will implement the following event imputation methodology for those with missing data:

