- If the participant's last observed data is prior to Day 21, then impute as an event with event day as day of last observed data +1.
- If the participant's last observed data is on or after Day 21, then no imputation for event will be done and participant remains censored at day of last observed data.

6.2.4. Proportion of Participants with Death (all cause) through Week 24

Descriptive statistics will be used to summarize proportion of death through Week 24 by treatment group using mITT1 populations. Treatment comparisons between groups will be presented as odds ratios with 95% confidence intervals and P-value based on logistic regression model (if data permit).

If zero counts are observed in either treatment group, the Fishers Exact test will be performed (instead of logistic regression) and p-value provided.

The participants enrolled under or after protocol amendment 6 will not include this summary.

6.2.5. Number of COVID-19 Related Medical Visits through Day 28

The number of COVID-19 related medical visits will be analyzed with a negative binomial regression model, using the log total number of days of data collection as the participant offset variable (if data permit). The resulting analysis will evaluate the difference in estimated rate of number of medical visits between treatment groups and the associated 95% CI. The analyses will be done using mITT1 populations.

6.2.6. Number of Days of Hospital and ICU Stay in Participants with COVID-19 Related Hospitalization

Health resource utilization data will be summarized by treatment group for each treatment. The analyses will be done using mITT1 populations. Descriptive statistics (ie, mean, median, range) will be used to summarize this endpoint.

The resulting analysis will provide the estimated difference in the average of number of days stayed in the hospital between treatment groups, with p-value and 95% confidence interval. The analyses will be done using the mITT1 population.

6.2.7. Proportion of Participants with Severe Signs/symptoms Attributed to COVID19 through Day 28

Participants will record a daily severity rating of their symptom severity over the past 24 hours based on a 4-point scale in which 0 is reported if no symptoms were present; 1 if mild; 2 if moderate; and 3 if severe. A participant with severe score for any targeted symptoms post-baseline will be counted as severe.

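### SAP Appendix 1 applies the symptom endpoint's Day 25 censoring rule to the per-protocol analysis of hospitalization or death, so participants who leave before Day 25 count as event-free while unobserved

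*SAP*

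**What the plan says.** **Appendix 1.** The supplemental PP row for hospitalization or death through Day 28 gives Kaplan-Meier and a log-rank test as the model, with the rule "Participants who discontinued the study before Day 28 without event will be censored at Day 25". The PP row for the primary symptom endpoint carries the identical sentence.

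**Where Day 25 comes from.** SAP Section 6.1.1.1 explains it: "Day 25 is the last possible day the symptom alleviation and resolution endpoints can be achieved", because the definition also uses the three following days. Section 6.1.1.2 then sets out, apart from the PP analysis, a further analysis of the symptom endpoint: "The primary endpoint will also be analyzed in which participants who discontinued the study before Day 28 without event will be censored at Day 25". That sentence names no analysis set.

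**How the SAP body treats hospitalization or death.** Section 6.2.3 counts events "during the first 28 days of the study" and estimates the risk in each arm "using the Kaplan-Meier method to take account of lost to follow-up". Its sensitivity analysis has two branches:
- If last data are before Day 21: "impute as an event with event day as day of last observed data +1".
- If last data are on or after Day 21: "participant remains censored at day of last observed data".

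**Analysis set.** Section 4 states: "For proportion of COVID-19 related hospitalization or death from any cause and all other efficacy endpoints, mITT1 will be used". It names PP only for the primary endpoint.

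**The concern.** Day 25 marks the last day on which a four-day run of alleviation can begin. Hospitalization or death has no such run, and an event can occur on any day to Day 28.

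The rule also changes direction when moved. Alleviation is a good outcome, so holding dropouts event-free to Day 25 is a cautious assumption. Hospitalization or death is a bad outcome, so the same rule assumes a good result for people nobody observed. Someone who leaves on Day 6 contributes 25 − 6 = 19 unobserved days at risk in which no event can be recorded. Kaplan-Meier needs a risk set of people actually under observation, so the estimated risk comes out too low.

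Two further problems follow. The PP result would differ from the main analysis in both population and censoring, so a discrepancy could not be put down to the PP restriction. In the primary-endpoint rows, Appendix 1 attaches the Day 25 dropout rule only to the PP row. A programmer working from the table would merge two analyses that Section 6.1.1.2 lists separately.

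**Working it through.** The documents give no figure for this analysis, so there is none to reproduce.

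**Inputs**
- Event rates: 8/329 = 2.43% on placebo and 2/333 = 0.60% on active treatment at the first interim analysis (Protocol Section 2.2.2). They serve here as an assumed truth. Difference 1.83 points.
- Dropout: 5% and 18%, the two planning rates in SAP Section 2.3. The 5% reproduces the enrollment target: 1880/0.95 = 1979, stated as approximately 1980.
- Assumed, because the documents are silent: events spread evenly over Days 2–14 or Days 2–28; dropout all on Day 1, all on Day 5, or uniform over Days 1–24; dropout independent of risk.

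**Formula.** The risk at Day 28 is 1 − Π(1 − d_t/R_t). Let F_t and G_t be the event and dropout fractions before day t, and e_t the event mass on day t. Observed events are d_t = e_t(1 − G_t).
- Censoring at the last observed day: R_t = (1 − F_t)(1 − G_t). This returns the true risk.
- Day 25 rule, for t ≤ 25: R_t = (1 − F_t)(1 − G_t) + E_t, where E_t is the fraction who left event-free before day t. The larger denominator lowers the risk.

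**Closed-form check.** If a fraction d leaves on Day 1 and all events fall before Day 25, the rule gives p(1 − d). At 5%: 2.432% × 0.95 = 2.310% and 0.601% × 0.95 = 0.571%, a difference of 1.739 points. The relative shortfall equals the dropout fraction.

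**Results under the Day 25 rule** (last-day censoring gives 2.432%, 0.601% and 1.831 points throughout)

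| Dropout | Events | Timing of dropout | Placebo % | Active % | Difference, points | Relative shortfall, placebo |
|---|---|---|---|---|---|---|
| 5% | Days 2–14 | Day 1 | 2.310 | 0.571 | 1.739 | 5.0% |
| 5% | Days 2–14 | Day 5 | 2.347 | 0.580 | 1.768 | 3.5% |
| 5% | Days 2–14 | Days 1–24 | 2.396 | 0.592 | 1.804 | 1.5% |
| 5% | Days 2–28 | Day 1 | 2.324 | 0.574 | 1.750 | 4.4% |
| 5% | Days 2–28 | Day 5 | 2.342 | 0.578 | 1.763 | 3.7% |
| 5% | Days 2–28 | Days 1–24 | 2.375 | 0.587 | 1.789 | 2.3% |
| 18% | Days 2–14 | Day 1 | 1.994 | 0.492 | 1.501 | 18.0% |
| 18% | Days 2–14 | Day 5 | 2.129 | 0.526 | 1.603 | 12.5% |
| 18% | Days 2–14 | Days 1–24 | 2.304 | 0.569 | 1.735 | 5.2% |
| 18% | Days 2–28 | Day 1 | 2.044 | 0.505 | 1.539 | 16.0% |
| 18% | Days 2–28 | Day 5 | 2.108 | 0.521 | 1.588 | 13.3% |
| 18% | Days 2–28 | Days 1–24 | 2.230 | 0.551 | 1.679 | 8.3% |

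The risk difference therefore moves by 0.03 to 0.09 point at 5% dropout and by 0.10 to 0.33 point at 18%.

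**Three rules on one example.** Of 1000 participants, 50 leave on Day 3 and 20 have events on Day 8.
- Last-day censoring: 20/950 = 2.11%.
- Day 25 rule: 20/1000 = 2.00%.
- Day 21 imputation of Section 6.2.3: 1 − (1 − 50/1000)(1 − 20/950) = 7.00%.

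**Unequal dropout.** Take a true risk of 1.5% in both arms, with 2% leaving one arm and 8% the other on Day 1. The rule gives 1.5% × 0.98 = 1.47% and 1.5% × 0.92 = 1.38%, a gap of 0.09 point where there is none.

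**Leavers on or after Day 25.** For a leaver on Day 25 the rule changes nothing. For leavers on Days 26 and 27 it discards one and two observed event-free days.

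**The case against.** The best defense is that little depends on this row. It is one supplemental analysis. Section 4 assigns the endpoint to mITT1, Section 2 of the SAP says all further p-values are nominal, and the Day 21 imputation already tests a harsh assumption about early leavers. With equal dropout the shift is towards zero, so it does not flatter the drug. All of that stands and limits the importance of the point. It does not make the rule right.

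Correct censoring would also not cure informative dropout. Assume a 2.2% baseline risk, with 5% leaving uniformly over Days 1–20 at ten times that risk (neither risk figure is from the documents). A simulation gave 2.76% under the Day 25 rule and 2.81% with last-day censoring, against a true 3.20%. The fix recovers 0.05 of a 0.44-point error.

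A reader might infer more than the documents support:
- **That Section 6.2.3 prescribes last-day censoring for every leaver.** Its explicit wording covers only last data on or after Day 21, within the sensitivity analysis; earlier leavers there are imputed as events. For the main analysis, last-day censoring is implied by the use of Kaplan-Meier and not spelled out.
- **That Section 6.1.1.2 places the Day 25 rule on mITT1.** It names no set.
- **That the risk is biased low wherever dropout occurs.** The understatement comes only from leavers before Day 25.
- **That the rule was copied from the symptom row.** The identical sentence makes this likely, but it remains an inference.

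**Conclusion.** The row is wrong as written. It states a rule with no basis for this endpoint, and following it gives a downward-biased risk whenever participants leave before Day 25. The row's PP set and log-rank test also lack support in Sections 4 and 6.2.3.

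The point is minor. At the current 5% planning rate the relative shortfall is about 1.5% to 5%, under 0.1 point in the risk difference. At the earlier 18% rate it is about 5% to 18%. These ranges rest on the interim rates as truth, the assumed timings, and dropout independent of risk. If leavers are at higher risk, the understatement against the true risk is larger, but most of that excess is common to both censoring rules.

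It would be a mistake to conclude that the main hospitalization or death result is compromised. The mITT1 main analysis, the multiple-enroller analysis and the vaccination-status subgroup rows carry no Day 25 rule.

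**What to change.** **Key secondary PP row.** Censor participants without an event at their last observed day, at most Day 28. Use the Kaplan-Meier difference of the main analysis in Section 6.2.3, and say explicitly that the Day 21 imputation does not apply. Either add the PP analysis and the log-rank test to Sections 4 and 6.2.3, or remove them from the row.

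**Primary-endpoint rows.** Give the PP analysis the main censoring rule of Section 6.1.1.1, and add a separate row for the Day 25 rule. State its analysis set; mITT1 is the natural choice because it is the primary set.

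**Cost.** Edits to the rule and model cells of one row and the rule cell of another, one new row, and a sentence or two in the SAP body. No new data are needed, and the main analysis does not change.
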